#### 11.5 Analysis of ECG Parameters

ECG is collected at baseline visit, and Week 16. ECG findings will be summarized by treatment group for each parameter and visit. Summaries will include n (%) of patients in following categories:

- Normal
- Abnormal – Not Clinically Significant
- Abnormal – Clinically Significant
- Unable To Evaluate
- Missing

## **12.0 Summary of Changes**

### **12.1 Summary of Changes Between the Latest Version of Protocol and the Current SAP**

The protocol planned statistical tests for baseline variables were removed sine it is not meaningful to conduct hypothesis test of randomization.

In the protocol, five models were proposed to be considered for MCP-Mod: linear,  $E_{\max}$ , exponential, logistic and  $\text{sig}E_{\max}$ . In the SAP, quadratic model was added as an additional candidate model.

In the protocol, DLQI is a secondary endpoint. Due to collection issues in DLQI Question 7, the corresponding secondary endpoints have been changed to exploratory variables and the answers to Question 7 will be removed from the analyses. Of note, correction to the DLQI ePRO device has been implemented while the study is ongoing. Additional analyses based on correct DLQI data may be performed.

Proportion of subjects achieving an improvement of 4 or more points from Baseline in pruritus NRS among subjects with a baseline of at least 4 was added as a secondary endpoint.

### **12.2 Summary of Changes Between the Previous Version and the Current Version of the SAP**

Not applicable. This is the first version of SAP.

---

### 0.0 Questionnaire

#### Body Area Affected:

The extent of AD is assessed as a percentage of each defined body area. To help in determining this extent, the sites affected by eczema are shaded on a drawing of a body. The rule of 9 is used to calculate the affected area (A) as a percentage of the whole body:

- Head and neck 9%
- Upper limbs 9% each
- Lower limbs 18% each
- Anterior trunk 18%
- Back 18%
- Genitals 1%

The score for each area is added up. The total area is 'A,' which has a possible maximum of 100%.

#### Symptom Severity:

A representative area of eczema is selected. In this area, the intensity of each of the following 6 specific symptoms is assessed as none (0), mild (1), moderate (2) or severe (3).

- Redness
- Swelling
- Oozing/crusting
- Scratch marks

- Skin thickening (lichenification)
- Dryness (this is assessed in an area where there is no inflammation)

The scores for these 6 specific symptoms should be added, for a maximum of 18 total points, assigned as "B" in the overall SCORAD calculation.

### Subjective Symptoms:

Subjective assessment of itch and sleeplessness is recorded for each symptom by the subject on a visual analogue scale (VAS), where 0 is no itch (or sleeplessness) and 10 is the worst imaginable itch (or sleeplessness), with a maximum possible score of 20. This parameter is assigned as "C" in the overall SCORAD calculation.

Visual analog scale  
(average for the last  
3 days or nights)

PRURITUS (0to10)		0	10
SLEEP LOSS (0to10)			

(10 cm in length)

## 1.0 Scoring Algorithm

The SCORAD is calculated as:  $A/5 + 7B/2 + C$ .

A-Total affected area

B-Symptom severity

C- Subjective assessment of itch and sleeplessness.

## 2.0 Missing Value Handling

If any of the components is missing, then the overall score will be treated as missing.

## 3.0 Efficacy Variables

- Changes from Baseline for the overall SCORAD score and the affected area scores of head/neck and genitals
- Achievement on pre-specified percentages of improvement, SCORAD 50/75/90 .

# 1.0 Patient Oriented Eczema Measure (POEM)

## 1.1 Questionnaire

POEM for self-completion

Patient Details: \_\_\_\_\_

\_\_\_\_\_

\_\_\_\_\_

\_\_\_\_\_

Date: \_\_\_\_\_

Please circle one response for each of the seven questions below about your eczema. Please leave blank any questions you feel unable to answer.

1. Over the last week, on how many days has your skin been itchy because of your eczema?

No days      1-2 days      3-4 days      5-6 days      Every day

2. Over the last week, on how many nights has your sleep been disturbed because of your eczema?

No days      1-2 days      3-4 days      5-6 days      Every day

3. Over the last week, on how many days has your skin been bleeding because of your eczema?

No days      1-2 days      3-4 days      5-6 days      Every day

4. Over the last week, on how many days has your skin been weeping or oozing clear fluid because of your eczema?

No days      1-2 days      3-4 days      5-6 days      Every day

5. Over the last week, on how many days has your skin been cracked because of your eczema?

No days      1-2 days      3-4 days      5-6 days      Every day

6. Over the last week, on how many days has your skin been flaking off because of your eczema?

No days      1-2 days      3-4 days      5-6 days      Every day

7. Over the last week, on how many days has your skin felt dry or rough because of your eczema?

No days      1-2 days      3-4 days      5-6 days      Every day

## 1.2 Scoring Algorithm

Each of the seven questions carries equal weight and the responses are scored from 0 to 4 as detailed below:

- 0 = no days
- 1 = 1-2 days
- 2 = 3-4 days
- 3 = 5-6 days
- 4 = Every day

Then take the sum of seven responses.

## 1.3 Missing Value Handling

If one question is left unanswered or scored “unable to answer” this is scored 0 and the scores are summed and expressed as usual out of a maximum of 28. If more than one question is left unanswered or scored “unable to answer” the questionnaire is not scored. If two or more response options are selected for a single question, the response option with the highest score should be recorded.

## 1.4 Efficacy Variables

- The sum of the seven questions will be analyzed by change from Baseline.

2.0 Medical Outcomes Study (MOS)

2.1 Questionnaire

## Your Sleep

For each of the following questions, please mark an  in the one box that best describes your answer.

1. How long did it usually take for you to fall asleep during the past 4 weeks?

0-15 minutes	16-30 minutes	31-45 minutes	46-60 minutes	More than 60 minutes
▼	▼	▼	▼	▼
 1	 2	 3	 4	 5

2. On the average, how many hours did you sleep each night during the past 4 weeks?

Write in number of hours per night:

3. How often during the past 4 weeks did you...

	All of the time	Most of the time	Some of the time	A little of the time	None of the time
	▼	▼	▼	▼	▼
a	feel that your sleep was not quiet (moving restlessly, feeling tense, speaking, etc., while sleeping)?				
	 1	 2	 3	 4	 5
b	get enough sleep to feel rested upon waking in the morning?				
	 1	 2	 3	 4	 5
c	awaken short of breath or with a headache?				
	 1	 2	 3	 4	 5
d	feel drowsy or sleepy during the day?				
	 1	 2	 3	 4	 5
e	have trouble falling asleep?				
	 1	 2	 3	 4	 5

**How often during the past 4 weeks did you...**

	All of the time	Most of the time	Some of the time	A little of the time	None of the time
f awakened during your sleep time and have trouble falling asleep again?.....	 1	 2	 3	 4	 5
g have trouble staying awake during the day?.....	 1	 2	 3	 4	 5
h snore during your sleep?.....	 1	 2	 3	 4	 5
i take naps (5 minutes or longer) during the day?.....	 1	 2	 3	 4	 5
j get the amount of sleep you needed?.....	 1	 2	 3	 4	 5

## 2.2 Scoring Algorithm

The 12-item MOS Sleep yields scores on six subscales, each consisting of one to four items

The subscales are:

- *Sleep Disturbance.* This four-item subscale addresses sleep initiation problems, as reported via the usual length of time to fall asleep and the frequency of trouble falling asleep, and sleep maintenance problems, as indicated by the frequency of experiencing sleep that was not “quiet” and the frequency of being awakened with trouble falling back to sleep.
  - Q#: 1, 3e, 3a, 3f
- *Sleep Quantity.* This single-item subscale represents the average number of hours the respondent sleeps each night.
  - Q: 2
- *Sleep Adequacy.* This two-item subscale asks about the frequency of awakening fresh and rested in the morning and the frequency of getting the amount of sleep needed.
  - Q: 3b
- *Somnolence.* Previously referred to as “Sleep Somnolence,” this three-item subscale measures how frequently during the day the respondent feels drowsy, takes naps, and has trouble staying awake.
  - Q: 3d, 3i, 3g

- *Shortness of Breath or Headache*. This single-item subscale asks about the frequency of awakening during the night with shortness of breath or with a headache. Q: 3c
- *Snoring*. This single-item subscale addresses the frequency of snoring during sleep.
  - Q: 3h

The sub-scores and overall score are calculated by the external vendor OPTUM, and thus no missing value algorithm is available in this document.

### **2.3 Efficacy Variables**

- The six sub-scores and the overall score will be analyzed by change from Baseline.

### **3.0 Pruritus Numerical Rating Scale (NRS)**

#### **3.1 Questionnaire**

#### **Pruritus/Itch Numeric Rating Scale**

0 1 2 3 4 5 6 7 8 9 10  
No Itch Worst Imaginable Itch

#### **3.2 Scoring Algorithm**

The daily pruritus NRS will be collected from patients electronically every evening via a hand-held device provided to the subject at Screening. A rolling weekly average is calculated..

#### **3.3 Missing Value Handling**

Missing values will not be imputed for the daily pruritus NRS.

#### **3.4 Efficacy Variable**

- Rolling average will be analyzed as percent change from baseline.
- Proportion of subjects achievement of a 4-point reduction will be analyzed.

## **4.0 Patient Global Impression of Severity (PGIS)**

### **4.1**

CCI

CCI

### **4.2 Scoring Algorithm**

PGIS is collected at site visits.

### **4.3 Missing Value Handling**

Missing values will not be imputed for PGIS.

[figure not shown]
### **4.4 Efficacy Variable**

PGIS will be analyzed by change from Baseline.

**5.0 Atopic Dermatitis Symptom Scale (ADerm-SS)**

**5.1** CCI

## 5.2 Scoring Algorithm

CCI

## 5.3 Missing Value Handling

Missing values will not be imputed for ADerm-SS. If any of Items CCI is missing then the CCI Score will be treated as missing.

## 5.4 Efficacy Variable

- For each of Items CCI changes from Baseline will be analyzed using the rolling CCI average.
- The CCI Score will be analyzed by change from Baseline.

## 6.0 Atopic Dermatitis Impact Scale (ADerm-IS)

6.1

CCI

CCI

## 6.2 Scoring Algorithm

CCI

## 6.3 Missing Value Handling

Missing values will not be imputed for ADerm-IS. If any of Items CCI is missing then the CCI Score- will be treated as missing.

## 6.4 Efficacy Variable

- For each of Items CC, changes from Baseline will be analyzed using the rolling CCI average.
- The CCI Score is analyzed by change from Baseline.

7.0 Asthma Symptoms Questionnaire

7.1 CCI [Redacted]

CCI [Redacted]

## 7.2 Scoring Algorithm

CCI

## 7.3 Missing Value Handling

The missing values of individual items will not be imputed. If response CCI is selected CCI, remaining items automatically become void. CCI No missing value imputation is performed for individual Items CCI

## 7.4 Efficacy Variables

[figure not shown]
- Items CCI will be analyzed by frequency and percentage of response categories.
- Item Ce and the summary score CCI will be analyzed by change from Baseline. The analysis will be performed only for subjects who had a response CCI at baseline.

## 8.0 Daytime Nasal Symptom Questionnaire

8.1

CCI

CCI

## 8.2 Scoring Algorithm

CCI

## 8.3 Missing Value Handling

If any of the responses is missing then corresponding summary score will be treated as missing.

## 8.4 Efficacy Variables

- CCI [redacted] will be analyzed by frequency and percentage of response categories.
- CCI [redacted] Symptoms and CCI [redacted] Scores will be analyzed by change from Baseline. CCI [redacted]

CCI

## **9.0 ActiGraphy Measurements**

Patient data on sleep activity and scratching events are collected daily with an electronic actigraphy device called Geneactiv Scratching Device. The measurements of interest downloaded from the device are total sleep time per night (TST min, in minutes), Sleep Efficiency (%), Wake After Sleep Onset (WASO, in minutes), and mean activity during rest (sleep). The parameter of interest related to scratching is events per hour. These five parameters will be analyzed by change from Baseline using the rolling weekly average.

## 10.0 Dermatology Life Quality Index (DLQI)

### 10.1 Questionnaire

DLQI is a simple 10-item questionnaire used to assess the handicap experienced by patients with various chronic skin diseases.

#### DERMATOLOGY LIFE QUALITY INDEX

DLQI

Hospital No:

Date:

Score:

Name:

Diagnosis:

Address:

The aim of this questionnaire is to measure how much your skin problem has affected your life OVER THE LAST WEEK. Please tick one box for each question.				
1	Over the last week, how itchy, sore, painful or stinging has your skin been?	Very much A lot A little Not at all	   	
1.	Over the last week, how embarrassed or self conscious have you been because of your skin?	Very much A lot A little Not at all	   	
2.	Over the last week, how much has your skin interfered with you going shopping or looking after your home or garden ?	Very much A lot A little Not at all	   	Not relevant 
3.	Over the last week, how much has your skin influenced the clothes you wear?	Very much A lot A little Not at all	   	Not relevant 
4.	Over the last week, how much has your skin affected any social or leisure activities?	Very much A lot A little Not at all	   	Not relevant 
6	Over the last week, how much has your skin made it difficult for you to do any sport ?	Very much A lot A little Not at all	   	Not relevant 
7 a	Over the last week, has your skin prevented you from working or studying ?	yes no	 	Not relevant 

7 b	If "No", over the last week how much has your skin been a problem at work or studying ?	A lot A little Not at all	  	
8	Over the last week, how much has your skin created problems with your partner or any of your close friends or relatives ?	Very much A lot A little Not at all	   	Not relevant 
9	Over the last week, how much has your skin caused any sexual difficulties ?	Very much A lot A little Not at all	   	Not relevant 
10	Over the last week, how much of a problem has the treatment for your skin been, for example by making your home messy, or by taking up time?	Very much A lot A little Not at all	   	Not relevant 

## 10.2 Scoring Algorithm

The DLQI measures six aspects of impaired dermatologic quality of life (Symptoms and feelings, Daily activities, Leisure, Work and School, Personal relationships, Treatment) and scores range from 0-30, with higher scores indicating more impaired quality of life.

**Table 1. Scoring of DLQI questions**

The scoring of each question is as follows:	
Very much A lot A little Not at all Not relevant Question unanswered Question 7: "prevented work or studying"	scored 3 scored 2 scored 1 scored 0 scored 0 scored 0 scored 3

The DLQI is calculated by summing the score of the 10 questions resulting in a maximum of 30 and a minimum of 0. The higher the score, the more quality of life is impaired. The DLQI can also be expressed as a percentage of the maximum possible score of 30

## 10.3 Missing Value Handling

For DLQI, missing values in individual questions are handled as follows.

- One Question unanswered this is scored 0 and the scores are summed and expressed as usual out of a maximum of 30.
- Two or more questions left unanswered – do not score questionnaire.
- If two or more response options (adjacent or non-adjacent) are checked for any question, the response option with the highest score will be entered into the database.
- If one item is missing from a two-item subscale that subscale should not be scored.
- If there is a response between two tick boxes, the lower of the two score options should be recorded. If there are responses between more than two tick boxes, the lowest of all the score options should be recorded.
- Question 7 is always counted as one question (for Abbott data management purposes only, the responses are coded in two sub-questions 7A and 7B.
  - When question 7A is “yes” then the score = 3 and question 7B is ignored.
  - When question 7A is “no”:
    - the score=2 if question 7B is “a lot”
    - the score=1 if question 7B is “a little”
    - the score=0 if 7B is “not at all”
    - the score=missing if 7B is not checked
  - When question 7A is “not relevant” and 7B is not checked, the score=0.  
If 7B is checked:
    - the score=2 if question 7B is “a lot”
    - the score=1 if question 7B is “a little”
    - the score=0 if question 7B is “not at all”
  - When question 7A is missing:
    - the score=2 if question 7B is “a lot”.
    - the score=1 if question 7B is “a little”.
    - the score=0 if question 7B is “not at all” or “not relevant”.
    - the score=missing if 7B is not scored.
  - When question 7A is “no” and “not relevant”, enter “not relevant” for question 7A.

#### **10.4 Efficacy Variables**

- Proportion of subjects with a DLQI 0 or 1 response.
- Change from Baseline in total DLQI score.

#### **10.5 Adjustment Accommodating Device Error in this Study**

During Period 1 of the study, there was an error in the device that Question 7.b) was displayed to a subject only when the subject answered “Yes” to Question 7.c). The error was corrected in August, with the baseline measurements being affected for all subjects, and the Period 1 post-baseline measurements being impacted for almost all subjects. In order to mitigate the bias caused by the device error, Items 7. a) and b) are excluded in calculating the total DLQI score for the Period 1 visits of all subjects.

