Within 35 days prior to the Baseline Visit, subjects will receive a full explanation of the study design and study procedures, provide a written informed consent, and undergo the screening procedures outlined in [Table 2](#). Lab values can be re-tested once during the screening period.

Beginning at the Screening Visit, twice daily use of an additive-free, bland emollient is required for at least 7 days prior to Baseline and during the study.

Subjects that initially screen fail for the study are permitted to re-screen once following re-consent. For additional re-screening, AbbVie Therapeutic Area Medical/Scientific Director approval is required. These cases must be brought to the attention of the AbbVie Therapeutic Area Scientific Director who will discuss with the AbbVie Medical Director as needed and provide a recommendation.

All screening procedures with the possible exceptions noted below will be repeated during re-screening. The subject must meet all the inclusion and none of the exclusion criteria at the time of re-screening in order to qualify for the study. There is no minimum period of time a subject must wait to re-screen for the study. If the subject had a complete initial screening evaluation including the assessment of an Interferon-Gamma Release Assay (IGRA; QuantiFERON Tuberculosis [TB] Gold In Tube test) or a purified protein derivative (PPD) test (or equivalent), or chest x-ray and electrocardiogram (ECG), these tests will not be required to be repeated for re-screening provided the conditions noted in [Section 5.2](#) are met and no more than 90 days have passed.

Period 1: 16-Week Treatment Period

Period 1 will begin at the Baseline Visit (Day 1) and will end at the Week 16 Visit. At the Baseline Visit, subjects who meet all the inclusion criteria and none of the exclusion criteria described in [Section 5.2.1](#) and [Section 5.2.2](#) will be enrolled into the study and randomized to double-blind treatment. During Period 1 of the study, subjects will visit

the study site at Baseline, Weeks 2, 4, 8, 12, and 16. A \pm 3 day window is permitted around scheduled study visits. Subjects will start on their respective dose at Baseline.

Twice daily use of an additive-free, bland emollient is required throughout Period 1.

Period 2: 72-Week Treatment Period

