## 6.0 Analysis Windows

### Definition of Baseline

Baseline refers to the last non-missing observation prior to the first dose of study drug. For randomized but not treated subjects, the baseline value will be the last non-missing measurement recorded prior to the randomization.

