## 10.5 Exploratory Variables

The following endpoints will be analyzed at all visits or weeks that the assessments are collected, except for daily assessments where results based on a rolling average by week will be presented.

- Time to EASI 50/75/90 and IGA "0" or "1" response in Period 1.
  - Proportion of subjects achieving EASI 50/75/90/100 response.
  - Proportion of subjects achieving SCORAD 50/75/90 response.
  - Change from Baseline in POEM at Weeks 4, 16, 24 and 40.
  - Change from Baseline at Weeks 4, 16, 24 and 40 in MOS Sleep Scale (Sleep Disturbance Score, Snoring Score, Short of Breath Score, Sleep Adequacy Score, Sleep Somnolence Score, Sleep Problems Index 1 Score, Sleep Problems Index 2 Score, Optimal Sleep Score, and Sleep Quantity Score).
  - Change from Baseline at Weeks 16 and 40 in Asthma Symptoms Questionnaire.
  - Change from Baseline at Weeks 16 and 40 in Daytime Nasal Symptoms Questionnaire.
  - Change from Baseline in total sleep time per night (TST min), Sleep Efficiency (%), Wake After Sleep Onset (WASO), number of scratching events per hour, mean activity during rest (sleep) periods as measured by actigraphy, by week until Week 40 and by visit thereafter.
  - Change from Baseline in ADERM-SS and ADERM-IS by week until Week 40 and by visit thereafter.
  - Change from Baseline in PGIS.
  - Proportion of subjects with a DLQI 0 or 1 response.
-

- Change from Baseline in DLQI.
- Change from re-randomization in EASI score in Period 2.

Primary and secondary variables will also be evaluated at all scheduled visits.

The efficacy of rescue will be summarized for subjects who received the rescue medication.

Due to collection issues in DLQI Question 7, the corresponding secondary endpoints have been changed to exploratory variables and the answers to Question 7 will be removed from the analyses. Of note, correction to the DLQI ePRO device has been corrected while the study is ongoing. Additional analyses based on correct DLQI data may be performed.

The EASI overall score, IGA and pruritus NRS score will be summarized at Baseline and Week 16 for subjects from Japan, with the percentage changes in EASI and pruritus NRS from baseline to Week 16.

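### The SAP has two conflicting rules for DLQI Question 7; taken literally, Appendix B sets 10-item Period 2 totals against a 9-item baseline

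*SAP*

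**What the plan says.** **The scoring instruction.** SAP Appendix B, 10.5 describes a display fault in the DLQI device during Period 1, corrected in August, "with the baseline measurements being affected for all subjects" and with nearly everyone's later Period 1 measurements affected too. Its remedy is that Items 7a and 7b "are excluded in calculating the total DLQI score for the Period 1 visits of all subjects". It does not mention Period 2. The general scoring rule in Appendix B, 10.2 stays in force: ten questions summed, with a maximum of 30.

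**The statement in the body of the SAP.** Section 10.5 (Exploratory Variables) and Section 12.1 (changes from the protocol) both say that "the answers to Question 7 will be removed from the analyses". Neither limits this to a period. Both demote the DLQI endpoints from secondary to exploratory. Section 10.5 adds: "Additional analyses based on correct DLQI data may be performed". It does not say which analyses.

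**What is analysed.** Appendix B, 10.4 lists the proportion with DLQI 0 or 1 and "Change from Baseline in total DLQI score". Section 10.5 opens: "The following endpoints will be analyzed at all visits or weeks that the assessments are collected". The exception that follows is for daily assessments and does not concern DLQI. SAP Table 9 gives Period 2 DLQI windows at Weeks 40, 52, 64, 76 and 88, with Week 16 as the entry value.

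**Where baseline sits.** SAP Section 6.0: "Baseline refers to the last non-missing observation prior to the first dose of study drug". Protocol Section 5.1: "Period 1 will begin at the Baseline Visit (Day 1) and will end at the Week 16 Visit". The baseline DLQI is therefore a Period 1 measurement.

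**The concern.** Appendix B, 10.5 is the only place that tells a programmer how to compute the total in view of the fault. Followed as written, with the ten-question default elsewhere, it gives a 9-item baseline and a 10-item total from Week 40 on. Subtracting one from the other adds the Question 7 score at the visit to every change score, always toward worsening. A programmer who follows Sections 10.5 and 12.1 instead gets a different set of Period 2 results from the same data, and nothing says which text governs.

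The outputs affected are those that Period 2 reports: descriptive within-arm changes from Baseline and, when read across periods, DLQI 0/1 rates. Protocol Section 5.6.1 gives evaluation of possible loss of response as one purpose of Period 2, so an apparent step toward worsening between Week 16 and Week 40 that comes from the scoring would be unwelcome. Because the fault touched every baseline, no valid 10-item baseline exists to put this right afterwards.

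**Working it through.** **Inputs.** Ten DLQI questions, each scored 0 to 3 (Appendix B, 10.2 and 10.3). Question 7 counts as one question. Baseline and Week 16 are Period 1 visits (Protocol 5.1; SAP Table 4). Week 16 is also Period 2 entry (SAP Table 9). Re-randomisation is 1:1 within each Period 1 group (SAP 4.2). The distribution of Question 7 scores is not given.

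**1. Scale maxima.** 10 × 3 = 30, which reproduces the stated maximum. Without Question 7: 9 × 3 = 27.

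**2. Change scores.** Let N be the 9-item total and S the Question 7 score; subscript b is baseline and v the visit.

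- 9 against 9 (SAP 10.5 and 12.1): N_v − N_b
- 10 against 10 (not obtainable, since S_b is faulty for everyone): (N_v + S_v) − (N_b + S_b)
- Mixed (Appendix B taken literally): (N_v + S_v) − N_b

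Mixed exceeds 9 against 9 by S_v, and exceeds 10 against 10 by S_b. Both lie between 0 and 3, and a positive shift means less improvement. The largest possible shift is 3/30 = 10% of the full scale.

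**3. Size of the within-arm shift.** The mean shift, relative to 9 against 9, equals the mean Question 7 score at the visit. As that mean is not given, the following values are assumptions:

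| Assumed mean Question 7 at visit | Mean shift (points) | Share of 30 |
|---|---|---|
| 0.25 | +0.25 | 0.8% |
| 0.5 | +0.5 | 1.7% |
| 1 | +1 | 3.3% |
| 2 | +2 | 6.7% |

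**4. Two worked subjects** (assumed N_b = 12, S_b = 2).

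- No real change, N_v = 12 and S_v = 2: 9 against 9 gives 0, 10 against 10 gives 0, mixed gives 12 + 2 − 12 = +2.
- Improved, N_v = 4 and S_v = 1: 9 against 9 gives −8, 10 against 10 gives −9, mixed gives 4 + 1 − 12 = −7.

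**5. Contrast between re-randomised arms.** The arm difference in mixed change is the difference in N_v − N_b plus the difference in S_v. The 10-against-10 contrast is the same less the difference in S_b. Under re-randomisation within a Period 1 group that last term is zero in expectation, so the two contrasts agree. A simulation of 400,000 subjects confirms it. Its assumed values were a mean 9-item change of −4 and −8 in the two arms, a mean baseline Question 7 of 1.0 in both, and a mean visit Question 7 of 0.9 and 0.3.

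| Scoring | Arm A | Arm B | B − A |
|---|---|---|---|
| 9 against 9 | −4.01 | −8.00 | −3.99 |
| 10 against 10 | −4.11 | −8.70 | −4.59 |
| Mixed | −3.11 | −7.70 | −4.59 |

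The mixed rule moves each arm's mean but gives the same contrast as 10 against 10.

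**6. DLQI 0/1.** A subject with N = 1 and S = 1 has a total of 1 under Period 1 scoring (a responder) and 2 under 10-item scoring (not a responder). No baseline enters this endpoint, so the effect is a change of definition between periods.

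**The case against.** The best defence is that the plan never says it will compare ten items with nine. Appendix B is silent on Period 2, and Section 12.1, the formal list of departures from the protocol, removes Question 7 outright. Under that rule there is no mismatch. This stands as far as it goes: the mixed comparison is one reading of a contradiction, and it cannot be stated as what the plan will do. It does not remove the point, because the reading comes from following the only explicit scoring instruction together with the default total.

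Three stronger readings are tempting, and the documents do not support them.

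- A reader might infer that different Question 7 scores in the two arms create a false treatment difference. In the simulation the mixed contrast is 0.60 points larger than the 9-item one (4.59 − 3.99). That gap is the assumed difference in work and study impairment at the visit (0.9 − 0.3), which the full instrument is meant to capture.
- A reader might infer that Period 2 DLQI 0/1 is biased. The 10-item version is the instrument as Appendix B defines it, and the 9-item version is the easier one to satisfy. Only comparison across the two periods is unsafe.
- A reader might infer a larger shift in arms with worse disease. Rescue can begin at Week 20, assessments after rescue are excluded (SAP 10.1.5), and the first scheduled Period 2 DLQI after entry is at Week 40. Who contributes Question 7 scores by then is unknown.

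It is also fair that the sponsor disclosed the fault and that Period 1 change from Baseline uses nine items on both sides under either rule.

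**Conclusion.** The point holds as an internal contradiction in the SAP that leaves Period 2 DLQI scoring unsettled. Under Appendix B taken literally, within-arm Period 2 change from Baseline is shifted toward worsening by the Question 7 score at the visit, 0 to 3 points per subject. The mean shift cannot be fixed from the documents. Under Sections 10.5 and 12.1 the shift is zero.

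The finding that randomised contrasts are spared assumes that all subjects compared at a visit are scored on the same items, and that baseline Question 7 is balanced by re-randomisation within the Period 1 group. It does not extend to imbalance that arises from rescue or dropout, which is a separate matter.

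A smaller loose end is that Appendix B sets its cut by period, while the fault ended on a calendar date. DLQI is also collected at premature-discontinuation visits, and the Week 40 window opens on Period 2 Day 2, so a Period 2 visit before the correction could keep a faulty Question 7. The documents do not say whether any did.

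Severity is low. DLQI is exploratory, Period 2 is summarised descriptively (SAP 10.1), and no primary, secondary or dose-response result depends on it.

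**What to change.** Amend Appendix B, 10.5 to agree with Sections 10.5 and 12.1:

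- Use the 9-item total, with Question 7 left out, at every visit for change from Baseline and for any DLQI 0/1 comparison across periods. State that this includes Week 16 when it serves as the Period 2 entry value.
- Report any 10-item Period 2 total, or 10-item DLQI 0/1, separately as a description of that visit, and only for visits after the device correction. This would give content to the optional analyses that Section 10.5 mentions.
- In the same edit, correct the reference to a Question 7.c), which the questionnaire in Appendix B does not contain.

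The cost is about one sentence of SAP text and a programming flag. The real loss is that Period 2 change scores no longer carry the work and study item. Since no valid baseline for that item exists, a like-for-like change could not have included it anyway.
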